**tDCS Montage:**

Ensure to mark electrodes for stimulation and that correct settings are adjusted on tES device. A 30 second ramp should be set. All impedances should be checked before stimulation is delivered. Ensure battery life is sufficient for stimulation for the day (2x20Min stimulation). Experimenters should remain blinded.

T8 -1.5mV; TP8,  
C6 & FT8 0.5mV

**EEG Tasks Directions:**

**Resting State**

*For the next 5 minutes you will be asked to sit still and keep your eyes on a small white fixation cross at the center of the screen. Try to keep your eyes centered on that and try not to move excessively.*

**Steady State**

For this last task, you will see a series of flashing black/white squares on the screen that will look like a strobe effect. They will appear in the center, left, right, or both sides of the screen but please try to keep your eyes focused on the plus sign in the center of the screen. You will also hear sounds during the task. Sometimes these sounds are played alone and other times they are played during the visual flashing.

### **Visual and Integration Assessments:**

Three visual assessments will be conducted for all participants: Biological motion and NES. These tests are run via **MATLAB**.

#### **Set-Up:**

##### **Bio Motion**

1. Connect Mac
  - a. Black thick wire (*taped and marked "TDCS"*) with Mac adaptor
2. Move the head and chin rest to be **75 cm from the monitor** (*marked with tape on the floor*)
3. Attach keyboard to computer and place on desk
4. Use alcohol wipe to clean:
  - a. Forehead and chin rest
  - b. Keyboard
5. Open up **"Visual Assessment Instructions"** PowerPoint
  - a. You will use this to describe the tasks to the participant
6. Open up **"MATLAB"**
  - a. Load in **"walker\_nonoise\_task.m"** and **"biomotionwalkerwithnoise.m"**

##### **NES**

1. .Open up **"MATLAB"**
  - b. Load in **"NES.m"**
2. Open up **"Visual Assessment Instructions"** PowerPoint
  - a. You will use this to describe the tasks to the participant

## **DATABASE Quality Assurance and Analysis**

The clinical database will be reviewed and checked for omissions, apparent errors, and values requiring further clarification using computerized and manual procedures.

## **Description of Study Endpoints**

### **Primary Endpoint**

Change from baseline to day 5 and 1 month in clinical measures (PANSS, UMPDHQ and AHRS) total score after 1 week of tES.

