# **Improving Hallucinations by Targeting the rSTS with tES**

**NCT #: NCT05165654**

**June 13, 2025**

Protocol Number:	2019P001016X
Title:	Improving Hallucinations by Targeting the rSTS with tES
Design:	Double blind, sham controlled design with baseline, day 5 and 1 month follow up visits during which tES (cathodal tDCS or sham) was delivered to the right superior temporal sulcus (rSTS) from baseline to day 5 each day (5 days) twice a day for 20 mins. Participants were randomly assigned to either active cathodal tDCS or sham condition to test the effectiveness and feasibility of stimulating the rSTS using a novel targeting methodology consisting of a lesion network guided brain target linked to hallucinations.
Objectives:	Evaluate the effectiveness and safety of tDCS for improving the positive and general symptoms associated with individuals who have a history of hallucinations
Enrollment:	12 Individuals
Clinical Sites:	Beth Israel Deaconess Medical Center, Boston, MA
Patient Population:	Male or female outpatients 18-50 years of age patient's diagnosis with either schizophrenia, schizoaffective disorder, or psychotic bipolar as defined by DSM-5 or DSM-IV-TR criteria
Primary and Secondary Outcomes:	Primary Outcomes: Positive and Negative Syndrome Scale (PANSS); University of Miami Parkinson's Disease Hallucinations Questionnaire (UMPDH-Q); Auditory Hallucinations Rating Scale (AHRS). Secondary Outcomes: Global Assessment of Functioning (GAF); Young Mania Rating Scale (YMRS); Symptom Checklist 90 (SCL-90) Biological Motion; Steady State EEG (Visual, Auditory and Multimodal); Brief Assessment of Cognition (BAC); Montgomery-Asberg Depression Rating Scale (MADRS); Neurological Evaluation Scale (NES); Biological Motion.

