Statistical Methodology:	Within and between comparisons to statistically detect differences in symptoms, visual/behavioral tasks and electrophysiology measures before and after treatment conditions (cathodal tDCS and sham). To determine the effectiveness and feasibility of targeting the rSTS with a novel targeting methodology to engage target outcomes.

**Statement:** The design, conduct and reporting of this trial shall be conducted in accordance with the protocol, the United States 45 Code of Federal Regulations (CFR) part 46 known as “The Common Rule”, 45 CFR 164.502(d), and 164.514(a)-(c) known as “The Privacy Rule” of the Health Insurance Portability and Accountability Act (HIPAA), and the International Conference on Harmonization (ICH)/Good Clinical Practice (GCP). All Investigators will have documented

training in The Collaborative Institutional Training Initiative (CITI Program) in Biomedical Research and GCP.

**Background:** Functional neuroimaging studies have identified neural correlates of hallucinations across multiple brain regions. Some studies suggest a common neuroanatomical substrate independent of the sensory modality, while others suggest different neural correlates for different types of hallucinations. However, whether these neuroimaging findings represented a cause, consequence or epiphenomenon of hallucinations was unclear until recently. Using lesion network mapping, researchers demonstrated that focal brain lesions play a causal role in the development of hallucinations and can occur in different brain locations, both inside and outside sensory pathway, and that greater than 90% of lesion locations causing hallucinations are negatively connected to the right superior temporal sulcus (rSTS). The rSTS is known to play a role in social cognition, biological motion, audiovisual integration, and speech. Hence, when spontaneous activity decreases at lesion locations causing hallucinations, spontaneous activity in the rSTS increases, the exact pattern thought to predispose to hallucinations. Additionally, functional connectivity within this region is abnormal in patients with visual and auditory hallucinations. Therefore, the association between rSTS connectivity and hallucinations would suggest this region may be optimal for modulation via non-invasive brain stimulation.

[figure not shown]
[figure not shown]

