## **OBJECTIVES**

### **Primary Objective**

The primary objective of this study is to evaluate the effectiveness of tDCS for improving the positive and general symptoms associated with individuals who have a history of hallucinations (PANSS, UMPDH-Q and AHRS).

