### **Clinical Assessments**

#### **Positive and Negative Symptom Scale (PANSS)**

The ratings are based on a clinical interview conducted by trained clinical staff, covering all of the items on the rating scale.

- This rating scale is meant to capture many different types of symptoms including positive, negative, and general psychopathology symptoms. The ratings are based on a clinical interview with the participants.
- Ratings should be based on the patient's condition in the past week.
- Always use the manual with anchor points when scoring and do not try to score from your memory of the anchor points or by their headings (mild, moderate or severe).

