#### **University of Miami Parkinson's Disease Hallucinations Questionnaire (UMPDH-Q)**

Administer questions on severity of hallucinations (1-6) and questions of quality of hallucinations (7-20). Each hallucination type (e.g. visual, auditory, tactile, olfactory) experienced derives an individual score. Higher total scores mean worsening symptoms.

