### **Primary Analyses**

Primary Analysis of the primary, secondary, and additional efficacy endpoints:

Mixed Model Repeated Measures analysis (MMRM)/non- parametric methods will be used to compare using within group differences as well as to determine the difference between the two treatment groups on the primary, secondary and safety endpoints depending on the distribution of the data.

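### Three scales at two visits are jointly primary, with no deciding test, success rule or multiplicity control

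*Combined protocol and SAP*

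**What the plan says.** The primary endpoint is "Change from baseline to day 5 and 1 month in clinical measures (PANSS, UMPDHQ and AHRS) total score after 1 week of tES". The synopsis lists the same three scales as primary outcomes, and the Primary Objective names all three; neither ranks them. That objective concerns effectiveness: "The primary objective of this study is to evaluate the effectiveness of tDCS for improving the positive and general symptoms". The synopsis gives a mixed purpose, "to test the effectiveness and feasibility of stimulating the rSTS using a novel targeting methodology", and its Statistical Methodology row repeats it. Planned enrolment is 12.

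The statistical plan consists of two short sections. General Statistical Considerations covers data capture, software and descriptive statistics by group. Primary Analyses names "Mixed Model Repeated Measures analysis (MMRM)/non- parametric methods", chosen according to how the data are distributed. It applies them both within groups and between the two arms, to primary, secondary and safety endpoints alike. Neither section gives an alpha, a success rule, a hierarchy, a composite or a multiplicity adjustment.

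Two definitions also bear on which score is primary. The endpoint uses the PANSS total, although of the PANSS the document says: "This rating scale is meant to capture many different types of symptoms including positive, negative, and general psychopathology symptoms". For the UMPDH-Q it says "Each hallucination type (e.g. visual, auditory, tactile, olfactory) experienced derives an individual score" and then refers to total scores.

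**The concern.** Effectiveness is the primary objective, but the plan does not say what result would meet it. After the data are seen, any of the three scales, either visit, or improvement within the active arm alone could be put forward as the primary finding. The last of these sets aside the sham control.

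Even the number of between-arm tests is open. It is six if each visit is tested, and three if the mixed model yields one treatment effect per scale across visits.

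The score definitions are a separate matter from the test count. The objective is about positive and general symptoms, whereas the PANSS total also contains negative symptoms. The document does not say how the separate UMPDH-Q scores for each hallucination type form the total.

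**Working it through.** The plan states no error rate or power, so there is no figure to reproduce. The check asks how often an ineffective treatment would give at least one nominally significant primary result.

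**From the document:** 3 scales × 2 visits = 6 change scores; 12 participants; two arms; MMRM or non-parametric methods; within- and between-group comparisons.

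**Assumed, because the document is silent:** 6 per arm; two-sided 0.05 per test; pooled t-tests with 10 df; normal data; none missing; no true effect; any one significant result may be claimed. Correlations between scales and between visits are unknown, so a range is used.

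**Independent case, by formula:**
- Favouring active, six tests: 1 − 0.975^6 = 0.141; three tests: 1 − 0.975^3 = 0.073.
- Either direction, six tests: 1 − 0.95^6 = 0.265; three tests: 1 − 0.95^3 = 0.143.

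**Correlated case, by simulation:** 200,000 null trials per setting, with the correlation matrix the Kronecker product of the scale and visit correlations. The three-test reading uses one t-test per scale on the mean of the two visits, as a stand-in for an overall mixed-model effect. Entries are the percentage of trials with at least one significant result.

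| Scale/visit correlation | 0/0 | 0.5/0.5 | 0.5/0.7 | 0.7/0.7 | 0.8/0.8 | 0.9/0.9 |
|---|---|---|---|---|---|---|
| Between arms, favouring active, six tests | 14.1 | 11.3 | 10.6 | 9.3 | 7.9 | 6.2 |
| Same, three tests | 7.3 | 6.3 | 6.4 | 5.6 | 5.1 | 4.4 |
| Between arms, either direction, six tests | 26.5 | 22.6 | 21.1 | 18.7 | 15.9 | 12.3 |
| Same, three tests | 14.3 | 12.7 | 12.9 | 11.4 | 10.2 | 8.6 |
| Favouring active, or improvement within active, six tests | 22.7 | 18.5 | 17.1 | 15.3 | 13.1 | 10.2 |
| Same, three tests | 12.1 | 10.5 | 10.6 | 9.3 | 8.5 | 7.3 |
| Rank-sum between arms, favouring active, six tests | 11.7 | 9.7 | 9.1 | 8.2 | 7.1 | 5.7 |
| Same, three tests | 6.0 | 5.3 | 5.4 | 4.8 | 4.4 | 3.9 |

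The single-test references are 2.5% favouring active and 5% in either direction. For the exact rank-sum test at 6 versus 6 (reject at U ≤ 5) the reference is 19/924 = 2.1% favouring active. The within-active rows use one-sample t-tests with 5 df and assume that neither arm changes. An 8:4 split moves the between-arm t-test rates by at most 0.3 points.

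**The case against.** Four points deserve weight.

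- **The top of the range is a bounding case.** Both visits are changes from the same baseline. With equal variances and equal between-visit correlations, two such change scores correlate 0.5. UMPDH-Q and AHRS also both cover auditory hallucinations. This stands: 14% is an upper bound. The rate is still about 11–13% with visit correlation 0.5 and scale correlation 0 to 0.5.
- **The inflation needs an any-one-counts rule, which the document does not state.** If every contrast had to be significant, the error rate could not exceed the 2.5% of a single test. That is correct, but the document does not state that rule either. A rule left open can be chosen after the results are known.
- **The simulated tests are not exactly the planned ones.** The three-test case is a stand-in for the mixed model, and floor effects and ties were not modelled; people with only a history of hallucinations, of any modality, may score low on AHRS. The within-active figures rest on no change in either arm, which is doubtful for symptom ratings, so they deserve less weight. The rank-sum rows lead to the same conclusion.
- **Consequences are limited.** With 12 people and a partly feasibility purpose, imprecision may matter more: a single t-test needs a standardised difference of 1.80 for 80% power. This stands and lowers the grade. It does not remove the point, because effectiveness is the stated primary objective and the document never calls the study a pilot or exploratory.

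**Conclusion.** The concern holds. The plan leaves open which result decides effectiveness, and provides no control over the several that could. Under the assumptions above, the chance of a false between-arm result favouring active rises from 2.5% to 6–14% on the six-test reading, or 4–7% on the three-test reading. Where in those ranges the truth lies depends on correlations the document does not give. The within-group tests and the method choice, for which no criterion is given, add further routes to a nominal finding. The inflation is moderate and the study small, so this is something the sponsor should fix rather than a critical fault. The PANSS mismatch is a separate and smaller definition point, and the UMPDH-Q scoring gap is minor missing detail.

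**What to change.** First establish whether outcomes have been seen by arm. The document does not settle this: the synopsis Design row describes assignment and stimulation in the past tense, while the tES description and Study Visits and Details use the future.

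**If outcomes have not been seen:** before unblinding, name one between-arm contrast (one scale, one exact score, one visit) as primary at two-sided 0.05. Which scale is the sponsor's choice. This also settles the six-or-three question. Test the other contrasts only if the primary is significant, in a stated fixed order or with Holm, and label within-group comparisons exploratory. The cost is wording only. The single primary keeps the full 0.05, and the chance of a false primary result favouring active returns to 2.5% at every correlation. Nominal results elsewhere no longer count as primary successes.

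**If outcomes have been seen:** report all six between-arm contrasts with confidence intervals and Holm-adjusted p-values, and label the effectiveness conclusion exploratory. Holm over six is demanding at 6 versus 6. The smallest p must be at most 0.05/6 = 0.0083, which an exact rank-sum test reaches only at U = 0 (2/924 = 0.0022) or U = 1 (4/924 = 0.0043). A t-test contrast with 80% power at 0.05 (standardised difference 1.80) has about 48% at 0.0083.

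**In either case:** reconcile the PANSS total with the objective's positive and general symptoms, and state or cite how the UMPDH-Q scores for each hallucination type combine into the total.

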### **Secondary Endpoints**

Change from baseline to day 5 and 1 month in GAF total score after 1 week of tES. Change from baseline to day 5 and 1 month in MADRS, YMRS, SCL-90, SCL-90 after 1 week of tES. Change from baseline to day 5 and 1 month in voltage for auditory, visual and audiovisual integration steady state measures after 1 week of tES. Change from baseline to day 5 and 1 month in cognition scores after 1 week of tES.

### **Safety and Tolerability Endpoint**

A self-rated questionnaire related to sensations of tES is given to participants after each stimulation.

### **General Statistical Considerations**

All collected study data will be collected on Redcap and processed using R and Matlab software. Descriptive statistics (n, mean, standard deviation, median, minimum and maximum) will be calculated by treatment group and sham group for continuous variables.

### **Primary Analyses**

Primary Analysis of the primary, secondary, and additional efficacy endpoints:

Mixed Model Repeated Measures analysis (MMRM)/non- parametric methods will be used to compare using within group differences as well as to determine the difference between the two treatment groups on the primary, secondary and safety endpoints depending on the distribution of the data.

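### Within-arm before/after comparisons stand beside active versus sham in the primary analysis, and nothing says which one decides effectiveness

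*Combined protocol and SAP*

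**What the plan says.** The Primary Analyses section opens with "Primary Analysis of the primary, secondary, and additional efficacy endpoints". It then says that MMRM or non-parametric methods "will be used to compare using within group differences as well as to determine the difference between the two treatment groups", and applies this to the primary, secondary and safety endpoints. The Statistical Methodology row of the synopsis has the same pairing: "Within and between comparisons to statistically detect differences in symptoms, visual/behavioral tasks and electrophysiology measures before and after treatment conditions". Neither place ranks the two comparisons.

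The Primary Objective is to "evaluate the effectiveness of tDCS for improving the positive and general symptoms associated with individuals who have a history of hallucinations", with no comparator. The Primary Endpoint is "Change from baseline to day 5 and 1 month in clinical measures" (PANSS, UMPDH-Q and AHRS totals), again with no comparator. The nearest the document comes to naming the deciding contrast is the Design row of the synopsis: "Participants were randomly assigned to either active cathodal tDCS or sham condition to test the effectiveness and feasibility of stimulating the rSTS". Enrollment is 12. The document gives no hypothesis, alpha level, allocation ratio or success criterion, and does not say that within-arm results are only supportive. It also lists no MMRM covariates, so it is open whether the baseline score is adjusted for.

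**The concern.** Randomisation and sham stimulation are there to separate the effect of tDCS from everything else that moves a symptom score over five days or a month: expectation, contact with staff, repeated rating and natural fluctuation. A before/after change in the active arm mixes all of these with any tDCS effect. Only the difference between arms removes them.

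As written, a report that the active arm improved significantly on AHRS could be presented as a result of the primary analysis even if the sham arm improved as much. Setting two within-arm results side by side (active significant, sham not) does not repair this, because it is not a test of the difference. With so few participants the two arms can easily fall on opposite sides of 0.05 by chance.

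**Working it through.** The document gives no power calculation or error rate to reproduce. Whether a governing contrast is named is settled by reading the objective, endpoint, design and analysis sections together, as set out above: none is. The arithmetic below shows what follows if a within-arm result is allowed to count.

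**Inputs.** From the document: 12 participants, two arms. Assumed: 6 per arm, two-sided 0.05, normally distributed change scores with SD 1 (so improvements are in SDs of the change score), no tDCS effect, one scale at one visit. The improvement *d* shared by both arms is unknown, so a range is shown.

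**Size of observed effect needed for significance.**
- Within one arm: t(0.975, 5)/√6 = 2.571/2.449 = 1.05 SD.
- Between arms: t(0.975, 10) × √(2/6) = 2.228 × 0.577 = 1.29 SD.

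The uncontrolled comparison has the lower threshold.

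**Probabilities with no tDCS effect.** The active-arm probability comes from the non-central t distribution with 5 df and non-centrality *d*√6. The pattern of active significant and sham not is P(active significantly improved) × [1 − P(sham significant in either direction)]. At 0.5 SD this is 0.169 × (1 − 0.171) = 0.140; at 0.8 SD it is 0.356 × (1 − 0.356) = 0.229. The between-arm rate and the last column come from simulation (400,000 trials per setting, pooled t-test with 10 df).

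| Shared improvement (SD) | Active arm significantly improved | Active significant, sham not | Active v sham significantly favours active | Active v sham also favours active, given active-arm improvement is significant |
|---|---|---|---|---|
| 0 | 2.5% | 2.4% | 2.5% | just under a third |
| 0.3 | 8.8% | 8.0% | 2.5% | 18% |
| 0.5 | 17% | 14% | 2.5% | 12% |
| 0.8 | 36% | 23% | 2.5% | 6.7% |

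The between-arm test rejects in either direction in 5% of trials in every row. With a 7:5 or 5:7 active:sham split at 0.5 SD, the pattern of active significant and sham not occurs in 17% or 11%.

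**Baseline covariate.** The variance of the adjusted arm difference relative to unadjusted change is ((1 + ρ)/2) × (1 + 1/(N − 4)). With N = 12 the second factor is 1.125. At a baseline/post correlation ρ of 0.3, 0.5, 0.7 and 0.8 the ratio is 0.73, 0.84, 0.96 and 1.01. The document gives no correlation.

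**The case against.** The strongest reply is that the design already settles the matter. The trial is randomised, double blind and sham controlled, with a stated purpose of testing effectiveness. The between-arm difference is planned, and nothing says a within-arm change will be taken as evidence. It is also fair that an endpoint is a participant-level variable and need not name a comparator, that the key sentence is poorly constructed and might partly refer to using change scores, and that in a 12-person study with a feasibility aim within-arm estimates have a legitimate use.

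Much of this stands. The design does point to active versus sham, and the absence of a comparator in the Primary Endpoint is weak evidence on its own. But a design description is not a decision rule. The synopsis removes most of the ambiguity in the key sentence: it says both kinds of comparison are meant to detect differences statistically, so the within-arm ones are inferential.

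A second objection is that separate t-tests are not the planned MMRM. A model with a common covariance would pool variance across arms, giving about 10 df at one visit. The within-arm threshold would then be 2.228/2.449 = 0.91 SD, and the active-arm rates at 0.5 and 0.8 SD would rise to about 20% and 43%. The figures above are therefore on the low side for that model. The non-parametric option was not modelled.

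The baseline covariate is a secondary matter. It does not bear on which contrast governs, and modelling baseline as a response is an accepted alternative.

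**Conclusion.** The concern holds and should be fixed. The randomised comparison is in the plan, so the trial is not undermined, but the plan does not prevent an uncontrolled active-arm change from carrying the effectiveness conclusion. Under the stated assumptions, the chance of an apparent benefit without any tDCS effect goes from 2.5% per scale and visit to 17% if both arms improve by 0.5 SD, and to 36% at 0.8 SD. If there is no shared improvement the excess disappears. The size therefore depends on an unknown quantity, and on the assumed split, alpha level and normality. That the plan ranks neither comparison depends on none of these.

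**What to change.** Add to Primary Analyses:

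> *The effectiveness conclusion rests only on the active-minus-sham difference in change from baseline, estimated from the arm and arm-by-visit terms of the MMRM, with the baseline score of the outcome as covariate and small-sample degrees of freedom. If a non-parametric method is used, the same between-arm contrast governs. Within-arm changes are reported as descriptive estimates with confidence intervals and are not evidence of effectiveness.*

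Reword the Statistical Methodology row of the synopsis to match.

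The cost is small: the data are the same, and the within-arm estimates remain available for feasibility and target engagement but can no longer support an efficacy claim. The baseline covariate uses one degree of freedom and gains no precision at a baseline/post correlation of about 0.8 or higher.

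This wording does not settle how the three scales and two visits are handled (3 × 2 = 6 between-arm contrasts), or how the choice between MMRM and a non-parametric method is made. Both need their own rule. The Design row is written in the past tense; if outcome data have already been unblinded, the change must be labelled post hoc.

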## **Study Visits and Details:**

Participants will complete baseline clinical, neuropsychological, visuoperceptual and neuro-physiological assessments (day 0), short-term follow-up (day 5) and long-term follow-up (month 1).

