**Self-Report tES Sensation Questionnaire**

Given a participant after each tES session (2x20min), the questionnaire measures severity of sensations felt during the stimulation. Rated on a scale from 0 (none) to 4 (severe). In addition, the questionnaire has an open-ended question to allow participants to express any additional sensations felt during stimulation.

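### The primary analysis lets the data's distribution pick the method and commits to no baseline adjustment; with 12 people, unadjusted change can carry part of a chance baseline gap

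*Combined protocol and SAP*

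**What the plan says.** The Primary Endpoint section defines the outcome as "Change from baseline to day 5 and 1 month in clinical measures", with PANSS, UMPDH-Q and AHRS total scores as those measures. The Secondary Endpoints section uses the same form, for example "Change from baseline to day 5 and 1 month in cognition scores after 1 week of tES". Study Visits and Details places the baseline assessments at day 0, so a baseline value exists for these measures. The synopsis gives an enrolment of 12.

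The inferential plan is the single sentence under Primary Analyses. MMRM or non-parametric methods "will be used to compare using within group differences as well as to determine the difference between the two treatment groups", and they do so "on the primary, secondary and safety endpoints depending on the distribution of the data". No non-parametric test is named, no criterion for the choice is given, and no model terms are listed.

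Two other places could have filled the gap and do not. The synopsis row on statistical methodology offers "Within and between comparisons to statistically detect differences in symptoms, visual/behavioral tasks and electrophysiology measures before and after treatment conditions". General Statistical Considerations names the software and says that descriptive statistics "will be calculated by treatment group and sham group for continuous variables".

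**The concern.** MMRM names a class of model, not its terms. Fitted to change scores, it may or may not include the baseline score, and a rank test on change scores makes no adjustment for baseline. If the arms happen to start apart, an unadjusted comparison of change mixes the treatment effect with regression to the mean, and the arm that starts worse will usually appear to improve more. With 12 people such gaps are common, and no stratification on severity is described.

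The open choice of method also allows a different method for each scale. The inclusion criteria admit people with only a history of hallucinations, while the AHRS rates hallucinations that are present now. Scores near zero on some scales, and hence different methods for different scales, are therefore plausible.

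**Working it through.** **Inputs.** From the documents: 12 participants, two arms, endpoints that are changes from baseline at day 5 and 1 month. Enrolment is given without alpha, effect size, SD or power, so there is no sample-size figure to reproduce. Assumed, because the documents do not state them: 6 v 6 allocation, a two-sided 5% level, results in baseline SD units, and a baseline to follow-up correlation rho of 0.3 to 0.85.

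**Step 1: how often the arms start apart.** The SD of the difference in baseline means is sqrt(1/6 + 1/6) = 0.577. P(|gap| > 0.5) = 2 × [1 − Φ(0.5/0.577)] = 0.386. The result depends little on allocation: 0.393 for 5 v 7 and 0.429 for 5 v 5.

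**Step 2: how much of the gap is carried.** Under bivariate normality, the expected difference in mean change given gap g is the treatment effect minus (1 − rho × SD_post/SD_base) × g. With equal SDs the fraction is 1 − rho. The mean gap, given that it exceeds 0.5, is 0.819. So the shift is 0.819 × 0.70 = 0.57, × 0.50 = 0.41, × 0.30 = 0.25, and × 0.15 = 0.12 SD.

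**Step 3: unequal SDs.** At rho 0.85 and an SD ratio of 0.7, the fraction is 1 − 0.595 = 0.405 and the shift is 0.33 SD. At a ratio of 1.3 it is 1 − 1.105 = −0.105, a shift of about 0.09 SD toward the arm that starts better. The direction is therefore not fixed at high rho.

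**Step 4: type I error and power by simulation.** Error rates are for trials with a gap above 0.5 SD. Repeated runs for normal scores agree to about 0.2 percentage points.

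| rho | 0.3 | 0.5 | 0.7 | 0.85 |
|---|---|---|---|---|
| Shift, unadjusted change (SD) | 0.57 | 0.41 | 0.25 | 0.12 |
| Type I error, unadjusted, normal scores | 8.8% | 7.7% | 6.7% | 5.9% |
| Same, exponential scores | 7.3% | 6.4% | 5.5% | 4.8% |
| Same, half of scores at the floor | 7.6% | 6.8% | 5.6% | 4.7% |
| Type I error, adjusted, normal scores | 5.0% | 5.0% | 5.0% | 5.0% |
| Power for 1 SD over all trials, unadjusted to adjusted | 26 to 34% | 35 to 40% | 52 to 54% | 81 to 79% |

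The adjusted shift is about 0 throughout. Over all trials, both analyses have type I error of 5.0 to 5.1% for normal scores.

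**Step 5: price of adjusting.** The variance ratio, adjusted to unadjusted, is (1 + 1/8)(1 + rho)/2 = 0.731, 0.844, 0.956 and 1.041. It equals 1 at rho = 2/1.125 − 1 = 0.778.

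**Step 6: choice by distribution.** A normality pretest deciding between a t test and an exact rank-sum test on change gave overall type I error of 4.4 to 5.0%.

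**Step 7: does the remedy hold up?** With two of 12 missing the 1-month visit, an adjusted MMRM with unstructured covariance and Kenward-Roger degrees of freedom had 1-month type I error of 4.6 to 5.7%. Its conditional shift was −0.02 to 0.03 SD, against 0.23 to 0.43 SD for unadjusted change. A baseline-by-visit term matters: with rho 0.85 at day 5 and 0.5 at 1 month, one common slope left a 0.24 SD shift at 1 month, against 0.00 with separate slopes.

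**The case against.** Unadjusted change is a valid analysis. Averaged over randomisation it has no bias and holds its 5% level, so the case against it rests only on trials that turn out imbalanced. That stands, and it is why this is an improvement to make rather than an error in the plan. It is also true that the inflation is smaller for skewed or floored scores and absent for them at rho 0.85, that adjustment loses a little power there, and that high rho over five days is plausible.

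Four stronger readings are tempting, and the documents do not support them.

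- That the plan omits adjustment. It is silent: an MMRM could carry baseline as a covariate or constrain the baseline means, and nothing rules this out.
- That letting the distribution choose the method inflates error. Step 6 shows that it does not, materially. The cost is analyst discretion and possible inconsistency between scales.
- That significance in the active arm alone would be taken as efficacy. Within-group comparisons are planned alongside the between-group one, and no section gives them that role.
- That the more favourable of two p-values would be reported. No section plans this.

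Timing also limits the benefit. The synopsis describes randomisation in the past tense, while the sections on tES and study visits use the future. If outcomes have been seen, the gain from fixing the method beforehand is lost. The adjusted estimate is still the better one to show.

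**Conclusion.** The concern holds in a limited form. The plan leaves the primary method to the distribution of the data and does not commit to using a baseline that it collects. The consequence is conditional: in about 39% of trials on any one scale, unadjusted change would be shifted by 0.57 SD at rho 0.3, falling to 0.12 SD at rho 0.85, with type I error of 8.8% falling to 5.9% for normal scores and about 7.5% falling to 4.8% for skewed or floored ones.

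These sizes rest on 6 v 6 allocation, equal SDs, and values of rho that the documents do not give. With unequal SDs the shift can be larger, or can reverse at high rho. The size in scale points cannot be worked out from the documents. The change should be made, because it is cheap and concerns the primary analysis. Confidence is medium, since the benefit depends on an unknown rho.

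**What to change.** For every endpoint with a baseline value, make one between-arm analysis primary whatever the distribution: MMRM with baseline score, arm, visit, arm-by-visit and baseline-by-visit. Report active minus sham at day 5 and at 1 month with 95% intervals.

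Replace the unnamed non-parametric alternative with one named check that is always reported and never triggered by a look at the distribution: a re-randomisation p-value from the same adjusted model, under the allocation procedure actually used. Label it a sensitivity analysis. Report the planned within-group changes as descriptive. If outcomes have already been seen, label the model as specified afterwards and show the unadjusted change result beside it.

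The cost is SAP wording and a short R script, with no new data. The statistical downsides are:

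- one degree of freedom per visit;
- slightly lower precision if rho exceeds about 0.78 with equal SDs (about 4% more variance at 0.85, where power for 1 SD goes from 81 to 79%);
- a somewhat conservative primary p-value for skewed or floored scores (type I error about 3 to 4%), which the re-randomisation result would show.
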